**LIST OF ABBREVIATIONS**

AE	Adverse event
ANCOVA	Analysis of Covariance
ANOVA	Analysis of Variance
CI	Confidence Interval
CRF	Case Report Form
CSR	Clinical Study Report
CTRS	Clinical Trial Registry Summary
EL.U/ml	ELISA unit per milliliter
Eli Type	Internal GSK database code for type of elimination code
ELISA	Enzyme-linked immunosorbent assay
ES	TVC
GMC	Geometric mean antibody concentration
GMT	Geometric mean antibody titer
GSK	GlaxoSmithKline
IU/ml	International units per milliliter
LL	Lower Limit of the confidence interval
MedDRA	Medical Dictionary for Regulatory Activities
N.A.	Not Applicable
PD	Protocol Deviation
PPS	Per Protocol Set
SAE	Serious adverse event
SAP	Statistical Analysis Plan
SBIR	GSK Biological's Internet Randomization System
SD	Standard Deviation
SR	Study Report
TFL	Tables Figures and Listings
TOC	Table of Content
UL	Upper Limit of the confidence interval

## 1. DOCUMENT HISTORY

Date	Description	Protocol Version
20-FEB-2018	first version	Administrative Change 1 Final: 06-SEP-2016

## 2. STUDY DESIGN

N: Number of subjects planned to be enrolled

Pre-vacc: Blood sample to be collected before the dose of the booster vaccination in pregnant women (Visit 1).

Post-vacc: Blood sample to be collected one month after the booster vaccination in pregnant women (Visit 2).

Protocol waivers or exemptions are not allowed with the exception of immediate safety concerns. Therefore, adherence to the study design requirements, including those specified in the outline of study procedures (Section 5.5 of protocol), are essential and required for study conduct.

- Experimental design: Phase IV, observer-blind, randomised, placebo-controlled, multi-centric, multi-country study with two cross-over groups. All eligible household contacts of the infants born to pregnant women enrolled in Spain will be eligible to receive a single dose of *Boostrix* as part of an assessment of cocooning.
- Duration of the study: The intended duration of the study will be approximately 5 months for each subject.
  - Epoch 001: Booster vaccination starting at Screening visit (Day -14 to 0) and ending at Visit 4 (post-delivery Month 2).

- Study groups: The study groups are defined as follows:
  - dTpa Group: This group will consist of pregnant women who will receive a single dose of *Boostrix* at 27-36 weeks (i.e. completed 27 weeks until 36 weeks) of gestation (Visit 1) and will receive a dose of the placebo post-delivery (within 72 hours).
  - Control Group: This group will consist of pregnant women who will receive a single dose of placebo at 27-36 weeks (i.e. completed 27 weeks until 36 weeks) of gestation (Visit 1) and will receive a dose of *Boostrix* post-delivery (within 72 hours).

The study groups and epoch foreseen in the study are presented in [Table 1](#)

**Table 1 Study groups and epoch foreseen in the study**

Study groups	Number of subjects	Age (Min/Max)	Epoch
			Epoch 001
dTpa Group	340	18 years - 45 years	x
Control Group	340	18 years - 45 years	x

The study groups and treatment foreseen in the study are presented in [Table 2](#)

**Table 2 Study groups and treatment foreseen in the study**

Treatment name	Vaccine name	Study Groups	
		dTpa Group	Control Group
Boostrix *	dTpa	x	x
Placebo for dTpa vaccine	Placebo	x	x

\*All eligible household contacts of the infants born to pregnant women enrolled in Spain will be eligible to receive a single dose of *Boostrix* as part of an assessment of cocooning.

- Control: placebo control
- Vaccination schedule:
  - All subjects will receive a single dose of *Boostrix* or placebo at 27-36 weeks (i.e. completed 27 weeks until 36 weeks) of gestation (Visit 1). Subjects who receive *Boostrix* at Visit 1 will receive a dose of placebo post-delivery (Visit 3) while those who receive placebo at Visit 1 will receive *Boostrix* post-delivery (Visit 3).
  - All eligible household contacts of the infants born to pregnant women enrolled in Spain will be eligible to receive a single dose of *Boostrix* as part of an assessment of cocooning. Although the vaccine can be administered anytime during the study, it is recommended that the vaccine is administered preferably 2 weeks before birth of the infant.
- Treatment allocation: randomised.
- Blinding: Observer-blind. Refer to Section 5.3 of protocol for details of the of blinding procedure.

The blinding of study epoch is presented in [Table 3](#)

**Table 3 Blinding of study epoch**

Study Epoch	Blinding
Epoch 001	observer-blind

- Sampling schedule: Blood samples will be collected at the following time-points:
  - Pre-Vacc (Visit 1): Before the booster vaccination, approximately 5 mL of blood sample will be collected from all subjects.
  - Post-Vacc (Visit 2): One month after the booster vaccination, approximately 5 mL of blood sample will be collected from all subjects.
  - Cord blood (Visit 3): approximately 2.5 mL of blood sample from the umbilical cord will be collected from all subjects.
- Type of study: self-contained
- Data collection: Electronic Case Report Form (eCRF).
- Safety monitoring: An independent data monitoring committee (IDMC) (including obstetrician, paediatrician, statistician and a neonatologist) will be put in place to oversee the safety aspects of *Boostrix* in the clinical study i.e. each SAE/congenital anomaly/foetal malformation case/incidence of grade 3 local and general solicited adverse events (AEs) will be reviewed by this committee (See Section 5.4.1 of protocol for details).

### 3. OBJECTIVES

#### Primary

- To demonstrate that the maternally transferred antibodies against pertussis in the dTpa Group is superior to that in the Control Group in terms of geometric mean concentrations (GMCs) for the pertussis antibodies, in the cord blood sample.

*Criterion:*

- The lower limit (LL) of the 95% confidence interval (CI) of the GMC ratio [dTpa Group divided by Control Group] for anti-pertussis toxoid (anti-PT), anti-filamentous hemagglutinin (anti-FHA) and anti-pertactin (anti-PRN) antibodies is  $\geq 1.5$ .

#### Secondary

- To assess the safety of a single dose of Boostrix in pregnant women, administered during 27-36 weeks of gestation, in terms of the outcomes of pregnancy and listed pregnancy-related adverse events of interest/neonate-related events of interest up to study end (Visit 4).
- To assess the immunogenicity of a single dose of Boostrix administered during pregnancy in terms of seropositivity status for antibodies against pertussis, in the cord blood sample.
- To assess the immunogenicity of a single dose of Boostrix administered during pregnancy in terms of seroprotection/seropositivity status, vaccine response and GMCs for antibodies against diphtheria, tetanus and pertussis, one month post-vaccination.
- To evaluate the reactogenicity of a single dose of Boostrix administered during pregnancy and post-delivery in terms of solicited symptoms during the 8-day (Day 0 – Day 7) follow-up period after vaccination.
- To assess the safety of a single dose of Boostrix administered during pregnancy and post-delivery in terms of unsolicited symptoms during the 31-day (Day 0 – Day 30) follow-up period after vaccination and serious adverse events (SAEs) during the period from Visit 1 up to Visit 4.
- To assess the acceptance rate of a single dose of Boostrix among eligible household contacts of the infants born to pregnant women enrolled in Spain, as part of an assessment of cocooning.
- To assess the safety of a single dose of Boostrix in terms of SAEs among the vaccinated household contacts of the infants born to pregnant women in Spain, as part of an assessment of cocooning, from the day of vaccination till 30 days after the vaccination.

## 4. ENDPOINTS

### Primary

- Immunogenicity with respect to components of the study vaccine, at delivery (in cord blood sample):
  - Anti-PT, anti-FHA and anti-PRN antibody concentrations.

### Secondary

- Outcome of pregnancy in terms of pregnancy outcomes up to study end (Visit 4).
  - Pregnancy outcomes will include live birth with no congenital anomalies, live birth with congenital anomalies, still birth with no congenital anomalies, still birth with congenital anomalies, elective termination with no congenital anomalies and elective termination with congenital anomalies.
- Outcome of pregnancy in terms of listed pregnancy-related adverse events of interest/ neonate-related events of interest up to study end (Visit 4).
  - Listed pregnancy-related adverse events of interest/ neonate-related events of interest will include gestational diabetes, pregnancy-related hypertension, premature rupture of membranes, preterm premature rupture of membranes, premature labour, premature uterine contractions, intrauterine growth restriction/poor foetal growth, pre-eclampsia, eclampsia, vaginal or intrauterine haemorrhage, maternal death, preterm birth, neonatal death, small for gestational age, neonatal hypoxic ischaemic encephalopathy and failure to thrive/growth deficiency.
- Immunogenicity with respect to components of the study vaccine received during pregnancy, one month post vaccination
  - Anti-D, anti-T, anti-PT, anti-FHA and anti-PRN seroprotection/seropositivity status and antibody concentrations.
  - Vaccine response to PT, FHA and PRN. Refer to section [11.2.4](#)
  - Vaccine response to anti-D and anti-T. Refer to section [11.2.4](#)
- Immunogenicity with respect to components of the study vaccine, in the cord blood sample.
  - Anti-PT, anti-FHA and anti-PRN seropositivity status.
- Solicited local and general symptoms (at Visit 1 and Visit 3).
  - Occurrence of each solicited local/general symptoms during the 8-day (Day 0- Day 7) follow-up period after the vaccination.
- Unsolicited adverse events (at Visit 1 and Visit 3).
  - Occurrence of unsolicited AEs within 31 days (Day 0 – Day 30) after any vaccination, according to the Medical Dictionary for Regulatory Activities (MedDRA) classification.
- Serious adverse events (SAEs).

- Occurrence of serious adverse events from Dose 1 up to study end (Visit 4).
- Percentage of household contacts of the infants born to pregnant women vaccinated in Spain who accepted *Boostrix* vaccine as part of an assessment of cocooning among the eligible household contacts.
- Occurrence of SAEs among the vaccinated household contacts of the infants born to pregnant women in Spain, as part of an assessment of cocooning, from the day of vaccination till 30 days after vaccination.

## **5. ANALYSIS SETS**

### **5.1. Definition**

#### **5.1.1. Total Vaccinated cohort**

- The Total Vaccinated cohort (TVC) analysis will be performed per treatment actually administered. A safety analysis based on the TVC will include all subjects with the study vaccine administration documented.
- An immunogenicity analysis based on the TVC will include all subjects vaccinated during pregnancy (Visit 1) for whom data concerning at least one immunogenicity endpoint measure is available.

#### **5.1.2. According-To-Protocol cohort for analysis of safety**

The ATP cohort for safety will consist of all subjects from the TVC who complied with vaccine administration up to the end of the Epoch 001, namely:

- Who have received the dose of study vaccine (at Visit 1) according to their random assignment,
- For whom administration site of study vaccine is known, and is according to protocol,
- Who have not received a vaccine not specified or forbidden in the protocol,
- For whom the randomisation code is not broken.

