### 5.1.3. ATP cohort for analysis of immunogenicity

The ATP cohort for analysis of immunogenicity will include all evaluable subjects from the ATP cohort for analysis of safety:

- Who meet all eligibility criteria.
- Who comply with the procedures and intervals defined in the protocol.
- Who are within the maximum interval allowed as defined in the protocol.
- Who do not meet any of the criteria for elimination from an ATP analysis (refer to Section 6.7.2 from protocol) during the study.
- Who did not receive a product leading to exclusion from an ATP analysis as listed in Section 6.7.2 from protocol.
- Who did not present with a medical condition leading to exclusion from an ATP analysis as listed in Section 6.8 from protocol.
- Who have the cord blood collection at least 21 days post-vaccination.
- For whom data concerning immunogenicity endpoint measures are available. This will include subjects for whom assay results are available for antibodies against at least one study vaccine antigen component one month after vaccination i.e. Visit 3 in the cord blood sample.

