**5.2.1.1. Elimination from ATP cohort for immunogenicity Excluded subjects**

A subject will be excluded from the ATP cohort for immunogenicity under the following conditions

Code	Condition under which the code is used
900	Questionable subject => Invalid informed consent or fraudulent data. In case informed consent is obtained retrospectively the subject is not eliminated.
1030	Study vaccine dose not administrated at all but subject number allocated => subjects enrolled but not vaccinated
1040	Administration of concomitant vaccine(s) forbidden in the protocol Previous vaccination containing diphtheria, tetanus or pertussis antigens or diphtheria and tetanus toxoids at any time during the current pregnancy.
1050	Randomisation failure (subject who received a vaccine not compatible with randomization)
1060	Randomisation code broken at the investigator site OR at GSK Safety department
1070	Site or route of study vaccine administration wrong or unknown.
1080	Vaccine has been administered (effective treatment number) despite a temperature deviation qualified by Status QA GMP NON Use.
1090	Vaccine has been administered (effective treatment number) out of the expiration date at the time of administration.
2010	Protocol violation linked to the inclusion/exclusion criteria including age and excluding codes mentioned below.
2040	Administration of any medication forbidden by the protocol
2050	Underlying medical condition forbidden by the protocol
2060	Concomitant infection related to the vaccine which may influence immune response
2070	Concomitant infection not related to the vaccine which may influence immune response
2090	Blood sample taken but non-compliance with blood sampling schedule for the cord blood sample (dates of BS not corresponding to adapted protocol intervals or unknown BS/vaccination dates) => Cord blood should be at least 21 days after vaccination
2100	Serological results not available for all antigens from the cord blood sample
2120	Obvious incoherence, abnormal serology evolution or error in data in cord blood sample (incoherence between CRF and results, wrong sample labelling.

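### Several ATP elimination rules have no cut-off at cord collection, and code 2100 is ambiguous, so valid primary-endpoint results can be removed without need

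*SAP*

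**What the plan says.** SAP section 4 sets the primary endpoint as anti-PT, anti-FHA and anti-PRN concentrations in cord blood at delivery. Section 6.3.1 analyses it on the ATP immunogenicity cohort.

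That cohort (5.1.3) is drawn from the ATP safety cohort (5.1.2): "all subjects from the TVC who complied with vaccine administration up to the end of the Epoch 001". Section 2 ends Epoch 001 at Visit 4, post-delivery Month 2. Of the bullets that follow, only the first carries a time limit: "Who have received the dose of study vaccine (at Visit 1) according to their random assignment". Another reads "Who have not received a vaccine not specified or forbidden in the protocol", with no date.

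The code list in 5.2.1.1 includes 1070, "Site or route of study vaccine administration wrong or unknown", and 2040, "Administration of any medication forbidden by the protocol". Neither names a dose or a date. The same is true of 1060 (code broken at the site or at the sponsor's safety department), 1080 (temperature deviation) and 1090 (expired product).

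SAP 5.1.3 also imports protocol 6.7.2, whose criteria on immunosuppressants, long-acting immune-modifying drugs, immunoglobulins and blood products run for the whole study. It requires compliance with the protocol's intervals as well. Protocol Table 6 ties ATP immunogenicity eligibility to those intervals and lists Visit 3 to Visit 4 at 45-75 days.

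On completeness of results, 5.1.3 keeps women for whom "assay results are available for antibodies against at least one study vaccine antigen component". Code 2100 removes a woman for "Serological results not available for all antigens from the cord blood sample".

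**The concern.** A cord concentration is fixed when the cord is sampled. Nothing that happens to the mother afterwards can change it: neither a mishandled post-delivery syringe, nor a transfusion in the puerperium, nor a late Visit 4. Rules that remove her for such events add nothing to the validity of the primary comparison and discard information.

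Code 2100 raises a different problem. Two programmers working from the same SAP could build different primary cohorts, one dropping only women with no cord result and the other dropping every woman with an incomplete set. At stake are a clearly defined primary analysis set and some precision.

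**Working it through.** **1. Which rules extend past the cord sample**

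| Rule | Limit stated | Can an event after the cord sample trigger it? |
|---|---|---|
| 5.1.2 assignment bullet; code 1050, which implements it | Visit 1 dose in 5.1.2 | Not if read together |
| Codes 2090, 2120 | Name the cord sample | No |
| Codes 2060, 2070; protocol 6.8 | Must be able to affect or alter the immune response | Not on a sensible reading |
| Code 1040 with protocol 6.7.2 | 30 days either side of the dose | Narrow, but which dose is not said |
| Codes 1070, 1080, 1090 | None | Yes, through the post-delivery injection |
| Code 1060 | None | Yes; protocol 8.6 unblinds unexpected, attributable SAEs whenever they occur |
| Code 2040; 6.7.2 drugs, immunoglobulins, blood products | Whole study | Yes |
| Table 6, Visit 3 to Visit 4, through 5.1.3 | 45-75 days | Yes, entirely after the cord sample |

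Two details make the open routes plausible. Protocol Table 17 assumes post-partum haemorrhage in 6.0% of women, and the glossary lists need for transfusion among its features. Protocol 4.3 excepts anti-D immunoglobulin at entry, but 6.7.2 does not repeat the exception. Separately, no SAP code enforces the Visit 3 to Visit 4 window, so the cohort definition and the code list disagree on it.

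**2. Reproducing the planned power**

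Inputs from protocol 10.3 and Table 16: 340 per group, 20% drop-out, one-sided alpha 0.025, margin 1.5. Anti-PT has SD 0.577 and true ratio 2.3; anti-FHA and anti-PRN have SD 0.564 and true ratio 5.

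- Evaluable: 340 × 0.80 = 272 per group.
- Anti-PT difference: log10(2.3/1.5) = 0.1856.
- Standard error: 0.577 × √(2/272) = 0.0495.
- Normal approximation: Φ(0.1856/0.0495 − 1.96) = Φ(1.79) = 96.3%; the noncentral t also gives 96.3%.
- Anti-FHA and anti-PRN: above 99.9% each.
- Overall, as 1 minus the summed type II errors: 96.3%. The protocol's figure of above 96% is reproduced.

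**3. Sensitivity to further loss**

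The documents give no loss rates, so these are assumed (noncentral t).

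| Further loss | N per group | Overall power | CI width on log scale, relative to N = 272 |
|---|---|---|---|
| 0% | 272 | 96.3% | 1.00 |
| 5% | 258 | 95.4% | √(272/258) = 1.03 |
| 10% | 245 | 94.5% | √(272/245) = 1.05 |
| 15% | 231 | 93.2% | √(272/231) = 1.09 |

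**4. The two readings of code 2100**

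Assume each antigen result is missing independently with probability m. Requiring every antigen drops 1 − (1 − m)³ of women; requiring at least one drops m³.

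| m | Every antigen required | Of 272 | At least one required |
|---|---|---|---|
| 1% | 3.0% | 8 | 0.0001% |
| 2% | 5.9% | 16 | 0.0008% |
| 5% | 14.3% | 39 | 0.0125% |

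Independence is itself an assumption. If antigens tend to be missing together, as when serum runs short, the readings lie closer. Incomplete sets are foreseeable: protocol 5.6.1.3.4 expects about 0.75 mL of cord serum, and 5.7.4.1 provides for insufficient volume.

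**5. The TVC trigger**

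SAP 6.3.1 adds a TVC analysis when 5% or more of vaccinated women with serology are excluded in a group. If all 340 have results, 17 exclusions (5.0%) trigger it and 16 (4.7%) do not.

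**The case against.** The other side has a good case, and much of it stands.

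- **The Epoch 001 sentence does not do this alone.** Its list specifies the Visit 1 dose, and the next bullet, on administration site, can be read as meaning the same dose. A reader might infer that any deviation at the post-delivery dose is excluded by that sentence; it is not. The open routes are the codes, 6.7.2 and Table 6.
- **Several codes limit themselves**, as the first table shows for 1050, 2060, 2070 and largely 1040.
- **The protocol wording is permissive.** Sections 6.7.2 and 6.8 say such events may lead to elimination. One cannot conclude that women were or will be dropped, only that the rules allow it. SAP 5.1.3, however, turns these into membership conditions without a cut-off.
- **Code 2100 has a harmless reading** that agrees with 5.1.3, and Template 11 counts N as subjects with available results. It is an ambiguity and not a contradiction.
- **Bias is not shown.** The groups receive different products after delivery, so a reader might infer that late eliminations distort the comparison. That would need elimination related to both group and cord concentration. The documents show no such link; wrong site, temperature deviation and expiry are logistical, and the laboratory is blinded.
- **The trial is not underpowered on this account.** The glossary equates evaluable with inclusion in the ATP analysis, so the 272 may already be net of eliminations, although protocol 10.3 attributes the 20% to early withdrawal.
- **A TVC analysis exists.** It is only a partial safeguard. It depends on the 5% trigger, it complements the primary analysis without replacing it, and it also readmits women excluded for good reason, such as those with a cord sample before 21 days.

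**Conclusion.** The point holds in a limited form. As written, codes 1060, 1070-1090 and 2040, the study-long criteria of protocol 6.7.2, and the Visit 3 to Visit 4 window applied through SAP 5.1.3 allow a valid cord result to be removed for an event after the endpoint was measured. Code 2100 leaves membership of the primary cohort open to two readings.

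The size is small. An assumed further loss of 5% takes overall power from 96.3% to 95.4%, and 10% takes it to 94.5%. These loss rates, and the per-antigen missing rates, are illustrations; the documents supply none. The protocol available is Amendment 2, while the SAP cites a later administrative change, so 6.7.2 and Table 6 are assumed unchanged. The reason to act is that the primary set should be defined unambiguously and the correction is almost free.

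**What to change.** Amend SAP 5.1.2, 5.1.3 and 5.2.1.1, for the cord endpoint:

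1. Apply administration codes 1050, 1070, 1080 and 1090 to dose 1 only.
2. Apply codes 1040, 1060 and 2040-2070, and the criteria of protocol 6.7.2 and 6.8, only to events dated up to cord collection. Codes 1040 and 1060 need a date rule because neither a concomitant vaccine nor a code break is a property of a study dose.
3. For the one-month endpoint, use the date of the Visit 2 sample as the cut-off.
4. State that the Visit 3 to Visit 4 interval does not affect cord eligibility, so that 5.1.3, the code list and Table 6 agree.
5. Reword code 2100 as no cord result for any of anti-PT, anti-FHA, anti-PRN (all three missing), and analyse each antigen on all women in the cohort who have that result.

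The cost is SAP text and elimination-code programming using event dates. No new data, sample size or endpoint is involved. The change should be in place before the codes are applied to unblinded data.
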